**OnCore**

**Please select the Library for your Protocol:**

This field is used in OnCore and determines the Reference Lists, Forms, Protocol Annotations, Notifications, and Signoffs available for the protocol. Protocols that require reporting to the NCI (National Cancer Institute), must select the Oncology library.

Oncology  
 Non-Oncology

**Protocol Application Type**

**Select the type of protocol you are creating:**

Please see additional criteria and information in the policy titled, "Reliance on the IRB of Another Institution, Organization, or an Independent IRB", on the [IRB web site](#).

Regular Study Application - Most common. The IRB will determine if the study is eligible for expedited review or requires full board review upon submission.  
 Application for Exemption from IRB Review - Includes Exempt, Not Human Subject Research, & Not Research.  
 External IRB Application - Any study using an external IRB as the IRB-of-Record.  
 Trainee Research While Away from Duke - Research conducted by medical students overseen by the Office of Curriculum & other student/trainee research away from Duke.

Individual Patient Expanded Access, Including Emergency Use - Use of an investigational product under expanded access, including emergency use of an investigational drug or biologic or emergency use of an unapproved device.

## Conflict of Interest

**Are any key personnel an inventor of any of the drugs, devices or technologies used in this research?**

Yes  No

**Do any key personnel have a conflict of interest management plan issued by DOSI-COI related to this research?**

Yes  No

## Oversight Organization Selection

**CRU (Clinical Research Unit) or Oversight Organization Selection:**

Please select the CRU.

Medicine

The Clinical Research Unit that takes responsibility for this study.

- Please select **Medicine** as the CRU **only** if the PI is in one of these Divisions or Institutes: Endocrinology, Gastroenterology, General Internal Medicine, Geriatrics, Hematology, Infectious Diseases, Nephrology, Pulmonary, Rheumatology & Immunology, Center for Applied Genomics and Precision Medicine, Center for the Study of Aging and Human Development, Duke Molecular Physiology Institute.
- More information on CRUs can be found on the Duke Office of Clinical Research (DOCR) website, <http://doctr.som.duke.edu>
- Questions concerning CRU selection should be directed to [[contact]](mailto:[contact]).
- For questions about the Campus Oversight Organization, please visit [\*\*Campus Oversight Organization\*\*](#).

## **EXTERNAL KEY PERSONNEL (KP) TOOL**

**Use the following External KP Tool to determine each time you consider adding outside Key Personnel. You will need to clear your responses to the following 2 questions each time.**

**List all Key Personnel on the study who are outside Duke if they are engaged in research and relying on the DUHS IRB: (Consider these questions every time you add external key personnel)**

**If you have additional personnel, use the External KP Tool as a guide to determine if the personnel are engaged in research. Only people ENGAGED IN RESEARCH should be added as external key personnel.**

Are the personnel intervening or interacting with the participant?

Yes  No

Are the personnel obtaining or receiving identifiable private information or protected health information (PHI)?

Yes  No

#### Indicate the Protocol source below:

The protocol source is the author of the protocol. If the protocol is a joint authorship between multiple sources, select the primary author.

An IRB fee may be assessed for all research that is supported by for-profit entities and requires full board review. For additional information, see the **IRB fees section of the IRB web site**.

- Duke PI initiated
- Commercial / Industry (for-profit entity) initiated
- Federal Government initiated
- Cooperative Group Initiated
- Foundation (non-profit group) initiated
- Other

## Sponsor and Funding Source

**Add all funding sources for this study: (Select 'Duke University' if you do not have funding or a sponsor for your study).**

View Details	Sponsor Name	Sponsor Type	Contract Type:	Project Number	Award Number
 Duke University	Duke University	Institutional	Grant		
Sponsor Name:		Duke University			
Sponsor Type:		Institutional			
Sponsor Role:		Funding			
Grant/Contract Number:					
Project Period:		From:08/30/2019 to:09/30/2020			
Is Institution the Primary Grant Holder:		No			
if No, then who is the Primary Grantee?		Neuroscience Translating Duke Health grant			
Contract Type:		Grant			
Project Number:					
Award Number:					
Grant Title:		Creating a clinical core model for the Alzheimer's Disease Research Center			
PI Name: (If PI is not the same as identified on the study.)					
Explain Any Significant Discrepancy:					
 National Institute on Aging	National Institute on Aging	Federal Government	Grant		1P30AG072958-01
Sponsor Name:		National Institute on Aging			
Sponsor Type:		Federal Government			
Sponsor Role:		Funding			
Grant/Contract Number:					
Project Period:		From:09/01/2021 to:06/30/2026			
Is Institution the Primary Grant Holder:		Yes			
Contract Type:		Grant			
Project Number:					
Award Number:		1P30AG072958-01			
Grant Title:		Duke/UNC Alzheimer's Disease Research Center			
PI Name:					

(If PI is not the same as identified on the study.)

Explain Any Significant Discrepancy:

### Is this a federally funded study?

Yes  No

### Does this study have any of the following?

- Industry sponsored protocol
- Industry funded Duke protocol
- Industry funded sub-contract from another institution
- Industry provided drug/device/biologic
- SBIR/STTR funded protocol

Yes  No

### As part of this study, will any samples or PHI be transferred to/from Duke to/from anyone other than the Sponsor, a Sponsor subcontractor, or a Funding Source?

Yes  No

### Is the Department of Defense (DOD) a funding source?

Yes  No

### For Federally funded studies:

#### Is your funding subject to, and does it comply with, the funding agency's policy for data sharing?

Yes  No

#### Check all that apply:

- NIH Genome Sharing - dbGaP
- NIH Genome Sharing - GWAS
- NIH Genome Sharing - NCI databases
- NIH Genome Sharing - other
- Non-NIH Genomic
- General Data Sharing

#### Enter the Grant Number or Other Federal Agency Proposal or Application Number:

1P30AG072958-01

**Note:** The Federal Funding Agency ID Number is the Sponsor's grant number assigned to your project and available on your Notice of Award (example: R01HL012345).

#### If known, enter the SPS (Sponsored Projects System) number if applicable:

0

**In the Initial Submission Packet, attach the following:**

- (1) The entire grant, or an explanation of why a grant is not needed.
- (2) NIH institutional Certificate form related to data sharing (if applicable).

**Mobile Devices and Software****Does this study involve the use of a software or a mobile application?**

Yes  No

**Please describe the following:**

- The developer of the mobile app and how the app will be obtained.
- What PHI will be collected via the app.
- Where the data will be stored and who will have access to it.

N/A

**List all software, including third party (non-Duke) and mobile apps, that will be utilized for ascertainment, recruitment, or conduct of the research/project: (eg, MaestroCare, DEDUCE):**

Duke Qualtric  
Duke Drop Box  
Duke REDCap  
PEDIGENE (part of ARENA data management system)  
Duke MaestroCare  
Sony ICD-UX560 or ICD-PX470 Stereo Digital Voice Recorder (or other similarly encrypted alternatives)  
GlobalApp  
VRFCAT (utilizing company provided iPads)

**Are you using FCAP (Federated Clinical Analytics Platform) for this study?**

Yes  No

**Multi-site Research****Is this a multi-site study?**

Yes  No

**Is the Duke PI/Co-PI the lead investigator or primary grant awardee?**

Yes  No

**Is the primary grant awardee a Duke employee?**

Yes  No

**Is a Duke employee the holder of the IND or IDE?**

Yes  
 No  
 N/A

**Is Duke the central coordinating center for this study?**

Yes  No

**Is Duke serving as a central statistical center for this study?**

Yes  No

**Is Duke serving as a central laboratory, reading center, analysis center or other central resource for this study?**

Yes  No

**Do you have ten or more sites?**

Yes  No

**Site Details**

Does the site have an IRB?	 Yes  No
Site IRB approval expiration date:	01/29/2026
If date not provided, explanation of why:	
Has the site granted permission for the research to be conducted?	 Yes  No
Does the site plan to rely on the DUHS IRB for review?	 Yes  No
What is the status of the study at this site?	 Open  Closed
Site approval letters or site personnel lists:	Attach site approval letters, site closure letters (if applicable), or site personnel lists in the Initial Submission Packet.

**Provide a description of the procedures that will be used to inform sites of unanticipated problems involving risks to subjects or others, interim results, protocol modifications and other information that may be relevant to the protection of subjects:**

The PI at Duke ([name]) will be the centralized contact to coordinate communication between the sIRB at Duke and other sites/local IRBs. She will spearhead monthly conference calls attended by the PIs at each site, as well as weekly meetings with the Clinical teams and Core Leaders. As relevant, additional team members, including Project Coordinators, will participate in such meetings. An agenda item will be included during each call for discussion or update regarding the single IRB arrangement. Participating sites will provide necessary information, assurances or adverse events to the Duke study team for submission to the Duke IRB and the respective local IRB. The Duke IRB office will communicate directly with the Duke PI and study team, with regular meetings to go over IRB-related issues. When appropriate, the Duke IRB office will communicate directly with the relying sites' Human Research Protection Program offices. Relying site (UNC) will follow local procedures to coordinate, collect, verify, and locally distribute information such as:

- Local context
- Conflict of Interest disclosure and management
- Completion of ancillary reviews
- Training and qualifications of study team (IRB, ethics)
- Continuing Review or Closure information
- Reportable Events

**How will you ensure that management, data analysis, and data safety and monitoring systems are adequate, given the nature of the research involved?**

The Duke Data Center (DDC) will work closely with the PIs and will oversee consistent application of scientific standards and methodological rigor for data collection, processing, entry, cleaning, and analytics. This will be accomplished by intensive training of all study staff, the development of well-defined study specific procedures (SSPs), and Manuals of Procedures (MOPs) with detailed instructions for procedures involved in data acquisition, processing, and upload to the REDCap platform. Fidelity to research procedures will be accomplished by the development of well-defined protocols and internal audits.

**How will you ensure that sample protocols and informed consent documents are developed and distributed to each collaborating institution?**

The Duke Site will:  
 Submit IRB application to sIRB. Distribute copies of IRB-approved documents to sites for editing and submission to local IRBs. Oversee and collect all required documentation and assurances (e.g., FWA to OHRP and reliance agreements) from sites for sIRB. Review and assist in site IRB applications for study as needed. Maintain records of IRB submissions, approvals, and expiration dates for all study sites. Provide guidance on IRB forms and track annual continuing reviews. Post IRB documents and regulator

documentation to central website. Distribute approved protocol changes/amendments to sites and develop SOPs to assure updates are distributed and receive IRB approval prior to initiation of any changes.

#### **How will you ensure that each collaborating institution holds an applicable OHRP-approved Assurance?**

Ongoing current proof of Site-specific IRB Assurance will be collected (and updated as warranted) from each site, and maintained at Duke.

#### **How will you ensure that each protocol is reviewed and approved by the IRB at the collaborating institution prior to the enrollment of subjects?**

Ongoing current proof of Site-specific IRB approval will be collected (and updated as warranted) from each site, and maintained at Duke. These approvals will be uploaded as part of continuing review submissions to the Duke IRB.

#### **How will you ensure that any substantive modification by the collaborating institution of sample consent information related to risks or alternative procedures is appropriately justified?**

Collaborating institution (UNC) will provide all approved consent versions back to the Duke site, and any significant modifications from the Duke provided template will be shared with the Duke IRB to confirm appropriateness prior to use with subjects.

#### **How will you ensure that informed consent is obtained from each subject in compliance with DHHS regulations?**

Subject consent will occur either electronically, stored directly in REDCap, or when completed on paper, will be scanned and uploaded into REDCap to allow for coordinating site consent review QC activities.

### **Research Abstract**

#### **Please type your Research Abstract here:**

The Research Abstract should summarize the main points of your study in one paragraph. The following guidelines may help you:

1. Purpose and objective (1-2 sentences)
2. Study activities and population group (2-4 sentences)
3. Data analysis and risk/safety issues (1-2 sentences)

The purpose of the study is to establish a clinical cohort for the Duke/UNC Alzheimer's Disease Research Center (ADRC). The cohort will be composed of subjects ages 25 to 44 at enrollment with normal cognition and subjects ages 45 to 80 at enrollment with normal cognition, mild cognitive impairment and a dementia diagnosis. Initial data including demographics, medical and family history, physical exam, neuropsychological testing will be obtained. Participants will most likely be asked to contribute a blood and urine sample, a cerebrospinal fluid sample, and undergo a MRI scan. The cohort ages 45 to 80 will be seen yearly until death to evaluate medical status, undergo neuropsychological testing and possibly collect additional samples or undergo additional imaging. All data will be de-identified and stored by the ADRC.

### **Research Summary**

#### **State your primary study objectives**

The primary objective is to create a clinical cohort for the Duke/UNC ADRC, enrolling 100 subjects per year until recruitment goals are met; thereafter we will enroll new participants only to replenish the cohort following subject death, withdrawal or loss to follow-up. The ages of the cohort will be 25 to 44 and 45 to 80 at the time of enrollment. Subjects ages 45 to 80 must have a project partner as part of the study. The cohort will undergo baseline data collection according to the current guidelines of the Uniform Data Set, set forth by the National Alzheimer's Coordinating Center including medical and family history, socioeconomic demographics, physical exam, neuropsychological testing, blood and urine sample, cerebrospinal fluid sample, and brain MRI. A subject's project partner can be substituted for another one,

and if so, the new potential project partner will be consented into the study. Subjects in the ages 45 to 80 group will be re-evaluated every year with a medical history update, physical exam and neuropsychological testing.

Additional blood, fluid or imaging may be requested at later dates. As part of their enrollment in the cohort the subjects will be presented yearly to a consensus committee to confirm diagnosis. A subset of the cohort ages 45 to 80, unable or unwilling to have the Lumbar Puncture, may alternately be offered to supplement a PET Scan to confirm diagnosis if/when AD symptoms are present.

The Duke/UNC ADRC obtained funding from the National Institute of Aging (NIA) in September 2021 and is an NIA designated ADRC program.

### **State your secondary study objectives**

- n/a

### **Please select your research summary form:**

Standard Research Summary Template

This is the regular (generic) research summary template which is required for all regular applications (unless your protocol fits under the other research summary templates in this category). Use of these instructions is helpful for ensuring that the research summary contains all necessary elements.

### **Standard Research Summary**

#### **Purpose of the Study**

- Objectives & hypotheses to be tested

The purpose of the study is to build a clinical cohort of adult research subjects with normal cognition, mild cognitive impairment (MCI) and dementia due to Alzheimer's disease and other related dementias (ADRD). The primary objective of this cohort will be to advance research on neurodegenerative brain disorders and the role of age, sex and genetics (especially APOE genotype) on their manifestation.

#### **Background & Significance**

- Should support the scientific aims of the research

Approximately 5 million Americans are currently suffering from Alzheimer's disease and related dementias (ADRD) with twice that number affected by mild cognitive impairment. Currently over \$100 million per year is spent on direct and indirect costs of caring for people with ADRD. Unless effective interventions are found the numbers of people with ADRD will continue to increase as the population ages.

Alzheimer's Disease Research Centers have been in existence since 1984 when Congress directed the National Institutes of Health (NIH) and the National Institute on Aging (NIA) to increase research on dementia. Dementia research continues to be a national priority. In 2011 Congress passed the National Alzheimer's Project Act with the primary goal of preventing and effectively treating ADRD by 2025. This act created increased funding opportunities for Alzheimer's Disease Centers to increase advances in the field through research and resource generation and sharing. In 2017, strategic planning by the NIA resulted in

recommendations including establishing new cohorts to build predictive models of disease and wellness and sharing of data, disease models and biological specimens for research purposes. Participants in a cohort should be well characterized with standardized clinical data collection and followed yearly until death.

As an NIA designated Alzheimer's Disease Research Center, the Duke/UNC ADRC is establishing a clinical cohort of research participants ages 25 to 44 who have a one time set of visit and a clinical cohort of research participants ages 45 to 80 who have a baseline set of visits and are followed yearly. Both groups will contribute biological samples kept in the ADRC repository.

This project will establish a clinical cohort at Duke and UNC with standard clinical data gathering and biological samples that can be used for current and future research studies at Duke and in the future, as part of collaboration with other Alzheimer's Disease Centers and national and international research projects including the National Central Repository for Alzheimer's Disease and Related Dementias (NCRAD) and the National Institute on Aging Genetics of Alzheimer's Disease Data Storage Site (NIAGADS).

## Design & Procedures

- Describe the study, providing details regarding the study intervention (drug, device, physical procedures, manipulation of the subject or the subject's environment, etc.). Discuss justifications for placebo control, discontinuation or delay of standard therapies, and washout periods if applicable. Identify procedures, tests and interventions performed exclusively for research purposes or more frequently than standard of care. Include alternative therapies, concurrent therapies discontinued per protocol, risk benefit ratio, and use of tissue/specimens. Discuss monitoring during washout periods if applicable. Include brief description of follow-up, if any.

Subjects with normal cognition, mild cognitive impairment and dementia diagnosis will be recruited from clinical visits at the Duke Neurology Memory Disorders Clinic at Moreeene Road. Subjects will also be enrolled by self-referral and active recruitment through participation in existing studies, registries, educational talks at community organizations and community health fairs. Subjects in the ages 45-80 cohort must have a dedicated project partner of their choice at time of enrollment. The project partner is an individual who knows the participant well, preferably a family member (e.g. spouse, adult child). Written informed consent will be obtained from all participants and their project partners (via paper or via eConsent). Besides answering questions about the participant, we are mandated to ask the project partners very basic demographic information about themselves. For example; race, ethnic background, gender, month & year of birth, years of education, relationship to participant, and type & frequency of contact with the participant. A potential subject screening log will be securely maintained, including potential subject Name, Contact Info (Email and Preferred Phone Number), Age (aggregated 89+), Race, Zip Code, Sex, Years of Education, Referral Source, and reason for non-enrollment (when applicable). The maintaining of a basic screening log is to ensure that we do not contact people multiple times, and to ensure equitable recruitment of people among race and education levels (via aggregate analyses).

Subjects will have an initial visit with information/history gathering, physical exam, neuropsychological testing and blood draw. The project partner will be asked questions about the participant's activities of daily living (ADL's), mood, and day to day behaviors. Subjects will have follow up visits coordinating imaging, lumbar puncture and donation of other biological samples. Either Lorazepam (0.5 to 1mg) or Alprazolam (0.25 to 0.5mg) will be prescribed at the request of the participant to help mitigate anxiety during the MRI and/or lumbar puncture. Both medications are taken by mouth, and subject will be informed they must have a driver present if they decide to take this medication prior to either of these procedures. Subjects also have the option to undergo an MRI simulation that closely mimics a real MRI scanner in terms of appearance, sensation, and sound. It features an automated table, lights, and a fan to enhance the realism of the experience. Additionally, the simulator can display tasks and playback MRI sounds, ensuring subjects are well-prepared and comfortable for the actual MRI scan.

Subjects and project partners in the ages 45 to 80 cohort will have an annual follow up visit as long as they are able to participate, preferably in person, but may also occur over the telephone if necessary.

All information gathered at the initial visit and annual follow up will be entered into the the current version of the Uniform Data Set (UDS), a longitudinal data set that is submitted to the National Alzheimer's Coordinating Center (NACC). At baseline and at yearly follow up, a consensus committee will meet to make a diagnosis based upon history and presentation, neuropsychological testing, imaging, and biomarker information.

All activities are research related. Subjects ages 25 to 44 and ages 45 to 80 will have a baseline visit which may contain tests including:

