### Data Management, Analysis and Statistical Considerations

- Describe endpoints and power calculations. Provide a detailed description of how study data will be analyzed, including statistical methods used, and how ineligible subjects will be handled and which subjects will be included for analysis. Include planned sample size justification. Provide estimated time to target accrual and accrual rate. Describe interim analysis including plans to stop accrual during monitoring. Phase I studies, include dose escalation schema and criteria for dose escalation with definition of MTD and DLT.
- For external collaborators/personnel** who are NOT ENGAGED in the research but are handling de-identified or a limited data set of **Duke** data, include their name, role and a description of the data.

A consensus committee will meet bi-weekly to monthly to review the clinical data gathered through the Uniform Data Set, imaging, and laboratory testing to determine a baseline consensus diagnosis for each subject enrolled in the cohort. Updated data on each subject will be reviewed yearly by the committee with an updated consensus diagnosis. Otherwise, there is no data analysis as part of the clinical cohort.

The goal is to enroll 100 subjects per year in the cohort, until recruitment goals are met. Thereafter, new participants will be recruited only to replenish the cohort due to death, withdrawal, or drop-out. Subjects

will otherwise participate in the clinical cohort until the time of death, withdrawal or drop-out. The purpose of this cohort and its collected data and samples is to serve as a resource for future study. There is no end point for the study.

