### Drugs, biologics, or other substances being evaluated as a part of this research study:

Add all drugs, biologics, or other substances being evaluated as a part of this research study for which an IND is provided for the indication used in this study.

Also add any other drugs, biologics or other substances here that are being used as a part of this research study, for which an IND is not provided.

*List every other drug, biologic or other substance for which side effects are described in the consent form.*

View	Drug Name	FDA Approved	A new drug or a new use of	IND Number
------	-----------	--------------	----------------------------	------------

Details			approved drug:	
	Drug/Biologic /Substance Alprazolam Generic Name: Generic Drug Name: Investigational Drug Name:	Yes	No	
	Drug/Biologic/Substance Generic Name:	Alprazolam		
	Generic Drug Name:			
	Investigational Drug Name:			
	Drug/Biologic/Substance Source:			
	Is the drug/substance being provided to the subject free-of-charge?	Yes		
	Is the Drug FDA Approved?:	Yes		
	Is this drug/biologic or other chemical, metabolite, nutritional substance or other substance to be used in this research subject to the provisions of the Controlled Substances Act?	No		
	Does this Drug have an IND Number?	No		
	IND Number			
	IND Holder:	N/A		
	IND details:			
	If FDA Approved and an IND is not required, Please provide a rationale for exemption:	This drug is used only for anxiety related to MRI and/or lumbar puncture. It is not being studied for safety and/or efficacy and is used according to its label.		
	Will drug/substance be shipped from Duke to external locations	No		
	Dose Range:	0.25-0.5 mg		
	Frequency:	once		
	Will this drug, biologic, chemical, metabolite, nutritional substance or other substance be manufactured or compounded at Duke?	No		
	Drug Storage Restrictions (including temperature, etc.):	None		
	As indicated in the Investigator's Brochure or other available documentation, what is the highest FDA Use-in-Pregnancy Rating for drug used for research purposes in this study?:	Category D		
	Drug/Biologic /Substance Lorazepam Generic Name: Generic Drug Name: Investigational Drug Name:	Yes	No	

Drug/Biologic/Substance Generic Name:	Lorazepam		
Generic Drug Name:			
Investigational Drug Name:			
Drug/Biologic/Substance Source:			

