Is the drug/substance being provided to the subject free-of-charge?	Yes		
Is the Drug FDA Approved?:	Yes		
Is this drug/biologic or other chemical, metabolite, nutritional substance or other substance to be used in this research subject to the provisions of the Controlled Substances Act?	No		
Does this Drug have an IND Number?	No		
IND Number			
IND Holder:	N/A		
IND details:			
If FDA Approved and an IND is not required, Please provide a rationale for exemption:	This drug is not being studied for safety and/or efficacy. It will be used according to label and provided to subjects who may require an anxiolytic for MRI and/or lumbar puncture		
Will drug/substance be shipped from Duke to external locations	No		
Dose Range:	0.5 mg		
Frequency:	once		
Will this drug, biologic, chemical, metabolite, nutritional substance or other substance be manufactured or compounded at Duke?	No		
Drug Storage Restrictions (including temperature, etc.):	None		
As indicated in the Investigator's Brochure or other available documentation, what is the highest FDA Use-in-Pregnancy Rating for drug used for research purposes in this study?:	Category D		

 Drug/Biologic /Substance PiB C11 Generic Name: Generic Drug Name: Investigational Drug Name:	No	No	
--	----	----	--

Drug/Biologic/Substance Generic Name:	PiB C11		
Generic Drug Name:			
Investigational Drug Name:			
Drug/Biologic/Substance Source:	UNC BRIC Radiochemistry Core		
Is the drug/substance being			

provided to the subject free-of-charge?	Yes			
Is the Drug FDA Approved?:	No			
Is this drug/biologic or other chemical, metabolite, nutritional substance or other substance to be used in this research subject to the provisions of the Controlled Substances Act?	No			
Does this Drug have an IND Number?	No			
IND Number				
IND Holder:	N/A			
IND details:	UNC Radioactive Drug Research Committee (RDRC) approval has been obtained and has been attached.			
If FDA Approved and an IND is not required, Please provide a rationale for exemption:				
Will drug/substance be shipped from Duke to external locations	No			
Dose Range:				
Frequency:				
Will this drug, biologic, chemical, metabolite, nutritional substance or other substance be manufactured or compounded at Duke?	No			
Drug Storage Restrictions (including temperature, etc.):				

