#### Who will be responsible for the storage, inventory and control of the drug/biologic or other chemical, metabolite, nutritional substance or other substance to be evaluated in this research?

The IDS is available to assist any investigator (upon request) with storage and control of investigational drugs in the outpatient setting

This drug will be prescribed to participants as needed for anxiety related to MRI and/or lumbar puncture. They will pick it up from their pharmacy as they would their usual prescriptions. The study will provide the drug free of charge to those who require this.

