#### Where will the drug/biologic or other chemical, metabolite, nutritional substance, or other substance to be evaluated in this research be stored?

N/A - drugs not being evaluated. Patient will get from their local pharmacy

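### The protocol gives two different upper doses of lorazepam for the same use: 1 mg in the procedures, 0.5 mg in the drug table

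*Protocol*

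**What the plan says.** Two places in the Protocol state a lorazepam dose.

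- **Design & Procedures:** "Either Lorazepam (0.5 to 1mg) or Alprazolam (0.25 to 0.5mg) will be prescribed at the request of the participant". The stated purpose is "to help mitigate anxiety during the MRI and/or lumbar puncture".
- **Drugs, Biologics, and Other Substances, lorazepam entry** (headed "Drug/Biologic/Substance Generic Name: Lorazepam"): the Dose Range field reads 0.5 mg and the Frequency field reads once. The reason given for needing no IND describes the same use: "It will be used according to label and provided to subjects who may require an anxiolytic for MRI and/or lumbar puncture".

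The alprazolam entry in the same table gives 0.25-0.5 mg, also once.

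Other sections set the context. On who will be eligible, Design & Procedures says: "Subjects with normal cognition, mild cognitive impairment and dementia diagnosis will be recruited". On supply, the protocol says: "They will pick it up from their pharmacy as they would their usual prescriptions". On storage it says: "N/A - drugs not being evaluated. Patient will get from their local pharmacy".

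**The concern.** Both statements are current, operative text about one drug for one purpose, and they set different upper limits. A prescription above 0.5 mg and up to 1 mg is within the procedures section but outside the range declared in the drug table. A prescriber, a monitor or the IRB could not tell from the document whether such a prescription follows the protocol.

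The drug table is more than a side note. The form asks for drugs used in the study without an IND to be listed there, and the reason for needing none sits in the same entry as the 0.5 mg figure. The drug is prescribed because of research procedures and the study pays for it, so the stated range is the protocol's responsibility even though the drug is not being tested.

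The population adds some weight. The cohort runs to age 80 at enrolment and includes people with mild cognitive impairment and dementia. The protocol already treats the drug's effect as material, since anyone who takes it must have a driver.

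**Working it through.** This is a comparison of text. No sample size, power or error rate is involved.

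**Inputs, side by side**

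| Drug | Limit | Design & Procedures | Drug table | Difference | Ratio |
|---|---|---|---|---|---|
| Lorazepam | lower | 0.5 mg | 0.5 mg | 0 mg | 0.5 / 0.5 = 1 |
| Lorazepam | upper | 1 mg | 0.5 mg | 1 − 0.5 = 0.5 mg | 1 / 0.5 = 2 |
| Alprazolam | lower | 0.25 mg | 0.25 mg | 0 mg | 0.25 / 0.25 = 1 |
| Alprazolam | upper | 0.5 mg | 0.5 mg | 0 mg | 0.5 / 0.5 = 1 |

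The only lorazepam dose common to both places is 0.5 mg. One cell pair out of four disagrees.

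**Could the conflict be only apparent?** Four readings were tried.

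1. *The 0.5 mg belongs to another drug.* It does not. The value comes after the lorazepam rationale about an anxiolytic and before the PiB C11 entry begins. The dose fields for PiB C11 and F-MK6240 are blank.
2. *The field holds only a starting or unit dose.* The field is labelled as a range, and the alprazolam entry fills it with a low and a high value that match the procedures section. A single figure for lorazepam therefore reads as the whole range.
3. *The 1 mg is the sum of one 0.5 mg dose for each of two procedures.* The protocol does not say this. Alprazolam carries the same frequency of once, yet its range is identical in both places, so the frequency wording does not account for a doubling.
4. *One of the two is superseded.* Neither place is an amendment log or a summary of changes.

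No other section of the protocol as available states a lorazepam dose, so nothing in it resolves the difference.

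**The case against.** The strongest counter-argument concedes the mismatch and disputes its weight. The drug is optional, prescribed individually and collected from the participant's own pharmacy. It is not under evaluation. Data Management, Analysis and Statistical Considerations states: "There is no end point for the study"; apart from the consensus diagnosis, no data analysis is planned. Safeguards exist as well: the driver requirement, the presence of project partners with participants who have dementia (Risk/Benefit Assessment), and documentation and review of adverse events by the principal investigator (Data & Safety Monitoring). On this view it is a clerical slip in one form field. Neither place calls its figure a maximum, and the consent form, which is not available here, might state a dose.

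Much of this stands as a limit on impact. Eligibility, data and analysis do not change, and the safeguards lower the practical risk. The statement that nothing reconciles the figures covers only the text at hand. But none of these points removes the conflict. The upper end of a stated range works as a limit whether or not it is called one. A consent form that gave a dose would leave the two protocol statements at odds with each other. The safeguards also do not tell a prescriber which range applies.

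**Conclusion.** The concern holds. The protocol contradicts itself on the upper lorazepam dose by 0.5 mg, a factor of 2; the lower limit and both alprazolam limits agree. The conclusion rests on reading the Dose Range field as the full range for the drug, which the alprazolam entry supports, and on both places being in force.

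It should be fixed but is modest in consequence. No endpoint or analysis depends on it. What remains open is which upper dose the protocol allows for an anxiolytic given around research procedures to a cohort that includes people with dementia.

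**What to change.** The responsible clinicians should reconcile the lorazepam range in Design & Procedures with the Dose Range field of the lorazepam entry under Drugs, Biologics, and Other Substances, so that the protocol states one range. Which figure is correct is theirs to decide, and no dose is proposed here. If the consent form states a lorazepam dose, it should be checked against the reconciled text at the same time.

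The cost is a text correction in one place, either the range in the procedures section or the form field, submitted for IRB approval like any other protocol change. The alprazolam entries need no change to their dose ranges, and nothing in recruitment, data collection or analysis is touched.
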